3.4. Multiple Assessments for the Same Assessment Time Point

In the case of multiple observations at a specific visit, the first non-missing measurement will be used for analysis, unless multiple study assessments are expected (eg, pre-dose vs post-dose). When multiple study assessments are expected, the first non-missing measurement for the visit and assessment time point will be used for analysis.

3.5. Multiple Study Centers

No adjustment for study center is planned.

3.6. Covariate Adjustment in Primary Analysis

No covariate adjustment will be made.

3.7. Sample Size Reassessment

Not applicable.

3.8. Interim Analyses

No interim analysis is planned for this study.

3.9. Timing of Final Analysis

To allow for reasonable duration on treatment to achieve a confirmed response, the final analysis for ORR will be conducted after all efficacy evaluable patients (defined in Section 3.12.3) have:

- undergone at least 4 post-baseline tumor assessments, or
- experienced radiological disease progression, or
- died or had clinical progression within 105 days of first dose of MIRV, or
- withdrawn from study for other reasons

It is estimated that the final analysis will be conducted approximately 6 months after the last patient is enrolled.

3.10. Test Sizes

For the primary endpoint of ORR, the null hypothesis that ORR is 12% will be tested against 1-sided Type I error (α) of 0.025. This study will reject the null hypothesis if the lower bound of 95% (2-sided) confidence interval (CI) for ORR is greater than 12%.

3.11. Hypothesis Testing and Multiple Comparisons

3.11.1. Primary Endpoint

In this single-arm study, hypothesis testing for the primary endpoint of ORR is performed using a confidence interval approach. Instead of reporting a p-value, 95% CI will be reported. Multiple comparison is not applicable.

3.11.2. Secondary Endpoints

The secondary endpoints of DOR, GCIG CA-125 response rate, PFS, and OS will be evaluated to further characterize the efficacy of MIRV. No formal hypothesis testing will be performed on secondary endpoints.

3.12. Analysis Populations

Six (6) analysis populations will be defined for use with various analyses. Table 2 illustrates the relationship between each population and the analyses for which the data from the population will be used. Baseline and patient disposition analyses will be conducted on efficacy evaluable population only if there is at least 5% difference between safety population and efficacy evaluable population.

Analysis Population	Analysis					
	Reason for Screen Failure	Baseline	Patient Disposition	Efficacy	Safety	PK Analysis
Screened	Х					
Safety		X	Х		Х	
Efficacy Evaluable by Investigator				Х		
Efficacy Evaluable by BICR				Х		
CA-125 Evaluable				CA-125 only		
PK Analysis Population						Х

Table 2:Analysis Populations

3.12.1. Screened

The Screened population includes all patients entered into the clinical database who have signed an informed consent.

3.12.2. Safety Population

All patients who received at least 1 dose of MIRV will be included in the Safety population.

3.12.3. Efficacy Evaluable Population

The Efficacy Evaluable population is defined as all patients in the Safety population who have measurable disease at baseline.

- Efficacy evaluable population for efficacy measurements based on investigator's assessment (ORR, DOR, PFS per investigator): this population includes all patients in the safety population who have measurable disease at baseline per investigator.
- Efficacy evaluable population for efficacy measurements based on BICR assessment (ORR, DOR, PFS per BICR): this population includes all patients in the safety population who have measurable disease at baseline per BICR.

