3. STUDY POPULATION

3.1. Criteria for Selection of Patient Population

3.1.1. Inclusion Criteria

1. Female patients ≥ 18 years of age
2. Patients must have a confirmed diagnosis of high-grade serous EOC, primary peritoneal cancer, or fallopian tube cancer

3. Patients must have platinum-resistant disease:
 - a. Patients who have only had 1 line of platinum based therapy must have received at least 4 cycles of platinum, must have had a response (CR or PR) and then progressed between > 3 months and ≤ 6 months after the date of the last dose of platinum
 - b. Patients who have received 2 or 3 lines of platinum therapy must have progressed on or within 6 months after the date of the last dose of platinum
Note: Progression should be calculated from the date of the last administered dose of platinum therapy to the date of the radiographic imaging showing progression
Note: Patients who are platinum-refractory during front-line treatment are excluded (see exclusion criteria)
4. Patients must have progressed radiographically on or after their most recent line of anticancer therapy
5. Patients must be willing to provide an archival tumor tissue block or slides, or undergo procedure to obtain a new biopsy using a low-risk, medically routine procedure for immunohistochemistry (IHC) confirmation of FR α positivity
6. Patient's tumor must be positive for FR α expression as defined by the Ventana FOLRI Assay
7. Patients must have at least 1 lesion that meets the definition of measurable disease by RECIST v1.1 (radiologically measured by the Investigator)
8. Patients must have received at least 1 but no more than 3 prior systemic lines of anticancer therapy, including at least 1 line of therapy containing bevacizumab, and for whom single-agent therapy is appropriate as the next line of treatment:
 - a. Adjuvant \pm neoadjuvant considered 1 line of therapy
 - b. Maintenance therapy (eg, bevacizumab, PARP inhibitors) will be considered part of the preceding line of therapy (ie, not counted independently)
 - c. Therapy changed due to toxicity in the absence of progression will be considered part of the same line (ie, not counted independently)
 - d. Hormonal therapy will be counted as a separate line of therapy unless it was given as maintenance
9. Patients must have an Eastern Cooperative Oncology Group Performance Status (ECOG PS) of 0 or 1
10. Patients must have completed prior therapy within the specified times below:

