10.1. Sample Size

Primary endpoint is confirmed ORR per Investigator assessment.

A sample size of 105 efficacy evaluable patients achieves 91% power to detect a difference in ORR of 12% (24% vs. 12%) using a 1-sided binomial test. The target significance level (1-sided α level) is 0.025. The actual significance level achieved by this test is 0.0242. These results assume that the ORR is 12% under the null hypothesis and 24% under the alternative hypothesis.

Patients who have received at least 1 dose of MIRV but are not efficacy evaluable will be included in Safety Analysis Population. However, these patients will not be included in the Efficacy Evaluable Population and will be replaced for the purpose of sample size determination. A total of approximately 110 patients will be enrolled to achieve 105 efficacy evaluable patients.

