At all post-baseline evaluations, the baseline classification (target, non-target) is to be maintained and lesions are to be documented and described in a consistent fashion over time (eg, recorded in the same order on source documents and CRFs).

For target lesions, measurements should be taken and recorded in metric notation. All tumor measurements must be recorded in millimeters.

At each assessment, a sum of the diameters (longest for non-nodal lesions, short axis for nodal lesions) for all target lesions will be calculated and reported. The baseline sum of the longest diameters (SLD) will be used as reference to further characterize any objective tumor regression in the measurable dimension of the disease. The lowest SLD (nadir) since, and including, the baseline value will be used as reference for evaluating progression.

After baseline, the actual size of the target lesion should be documented, if possible, even if the lesions become very small. If in the opinion of the radiologist, the lesion has likely disappeared, 0 mm should be recorded. If the lesion is present but too small to measure, an indicator of “too small to measure” will be provided on the CRF (a default value of 5 mm will be imputed during analysis).

Non-target lesions are to be assessed qualitatively (present, resolved, or unequivocal progression) and new lesion, if any, are to be documented separately.

At each evaluation, a time point response is to be determined for target lesions, non-target lesions, new lesions and overall.

Time Point Response Criteria

Target Lesion Time Point Response (TPR)	
Complete Response (CR)	Disappearance of all target lesions. All pathological lymph nodes (whether target or non-target) must have reduction in short axis to < 10mm.
Partial Response (PR)	At least 30% decrease in the sum of diameters (SoD of target lesions, taking as reference the baseline SoD
Progressive Disease (PD)	At least a 20% increase in the SoD of target lesion, taken as reference the smallest (nadir) SoD since and including baseline. In addition to the relative increase of 20%, the SoD must also demonstrate an absolute increase of at least 5 mm.
Stable Disease (SD)	Neither sufficient shrinkage to qualify for PR nor sufficient increase to qualify for PD.
Not Applicable (N/A)	No target lesions identified at baseline
Unable to Evaluate (UE)	One or more target lesions are not imaged and the remainder of the SoD compared with the nadir SoD does not meet the criteria for PD

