If the target lesion for a patient meets the criteria for both PR and PD at a given time point, the target lesion response is PD. If the nadir SoD is 0 (ie, the patient had a prior target lesion CR), the re-appearance of any prior target lesions to any degree constitutes PD.	
Non-Target Lesion TPR	
Complete Response (CR)	Disappearance of all non-target lesions and normalization of tumor marker level if tumor marker at baseline is above the upper normal limit. All lymph nodes must be non-pathological in size (< 10 mm short axis)
Non-CR/Non-PD	Persistence of one or more non-target lesion(s) and/or maintenance of CA-125 above the normal limits if CA-125 at baseline is above the upper normal limit
Progressive Disease (PD)	Unequivocal progression of non-target lesions. Unequivocal progression should not normally trump target lesion status. It must be representative of overall disease status change, not a single lesion increase.

Not Applicable (N/A)	No non-target lesions identified at baseline
Unable to Evaluate (UE)	One or more non-target lesions are not imaged and the remaining non-target lesions do not meet the criteria for PD

If the target lesion for a patient meets the criteria for both PR and PD at a given time point, the target lesion response is PD.
 
If the nadir SoD is 0 (ie, the patient had a prior target lesion CR), the re-appearance of any prior target lesions to any degree constitutes PD.
	
New Lesion TPR	
Yes	Lesion present at follow-up visit either for the very first time or re-appearing (ie, lesion was present at baseline, disappeared at a follow-up visit and re-appeared later).
No	No new lesions present at follow-up
Unable to Evaluate (UE)	Patient non assessed or incompletely assessed for new lesion

Determining Overall TPR

Target Lesion TPR	Non-Target TPR	New Lesions TPR	Overall TPR
CR	CR or NA	No	CR*
CR	Non-CR/non-PD	No	PR*
CR	UE	No	PR*
PR	Non-PD or NA or UE	No	PR*
SD	Non-PD or NA or UE	No	SD
UE	Non-PD	No	UE
PD	Any	No or Yes or UE	PD
Any	PD	No or Yes or UE	PD
Any	Any	Yes	PD
NA	CR	No	CR*
NA	Non-CR/non-PD	No	Non-CR/non-PD
Non-PD	Non-PD	UE	UE

CR, complete response; PR, partial response; SD, stable disease; PD, progressive disease; UE, unable to evaluate; NA, not applicable (no such lesions at Screening); Any, CR, PR, SD, PD, NA or UE.

The overall response at a given time point does not depend upon the overall response assigned at any prior time point.

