5. EFFICACY ANALYSES

The main efficacy analyses will use data from the Efficacy Evaluable population based on investigator's assessment. Sensitivity analyses will be performed with BICR assessment.

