5.1.1.1. ORR

The ORR will be calculated as the number of patients with a confirmed BOR of CR or PR divided by the number of patients in the Efficacy Evaluable population. Patients without at least 1 post-baseline RECIST assessment will be treated as non-responders (ie, these patients will contribute to the denominator, but not the numerator).

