5.5. Additional Sensitivity Analyses

Analysis of ORR, DOR, and PFS as assessed by BICR will be performed as sensitivity analysis using the same methods described in the previous sections.

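### The blinded (BICR) sensitivity analysis of the primary ORR changes reader and denominator together; a BICR ORR on the investigator-defined set should be added beside it

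*SAP*

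**What the plan says.** SAP 5 names the main analysis set: "The main efficacy analyses will use data from the Efficacy Evaluable population based on investigator's assessment". SAP 3.12.3 then defines a separate set for ORR, DOR and PFS read centrally: "this population includes all patients in the safety population who have measurable disease at baseline per BICR". SAP Table 2 lists the two as distinct populations.

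SAP 5.1.1.1 defines ORR as confirmed responders "divided by the number of patients in the Efficacy Evaluable population". SAP 5.5 says that the BICR analyses "will be performed as sensitivity analysis using the same methods described in the previous sections" and names no other denominator. Neither document plans a BICR ORR on the investigator's set, an investigator ORR on the BICR set, or a cross-table of the two reads.

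Two protocol provisions determine how the sets can differ:

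- Inclusion criterion 7 (Protocol 3.1.1) requires a lesion that meets the definition of "measurable disease by RECIST v1.1 (radiologically measured by the Investigator". Central agreement is not needed for entry.
- Protocol Appendix B defines PR on target lesions: "At least 30% decrease in the sum of diameters (SoD of target lesions, taking as reference the baseline SoD". In its table for the overall time point response, a patient whose target-lesion entry is "NA, not applicable (no such lesions at Screening" can reach CR, non-CR/non-PD or PD. There is no route to PR.

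Protocol 7.13.1 describes the central review as a sensitivity analysis of the investigator's ORR and DOR.

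**The concern.** A sensitivity analysis is most informative when it changes one thing. Here that should be the reader: the trial is open-label and single-arm, the primary endpoint is read by the investigator, and BICR is the only blinded read planned. As written, the patient set changes too. If the two ORRs differ, part of the gap may come from who was counted. If they agree, part of the agreement may come from the same source.

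The change of set is also not neutral. The patients most likely to drop out of the BICR denominator are those treated on investigator measurability whose lesions central review rejects. Because they cannot be BICR partial responders, they will mostly be BICR non-responders, and removing them tends to move the BICR rate up. What is at stake is how clearly the blinded check can be read. No decision rule depends on it.

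**Working it through.** **The plan's own figures.** With 105 evaluable patients, a null ORR of 12%, an alternative of 24% and one-sided alpha 0.025, the exact binomial test rejects at 20 or more responders. Its actual alpha is 0.0242, as stated in Protocol 10.1 and SAP 2.2.2. Its power is 90.6%, consistent with the 91% and 90% given there. The Clopper-Pearson lower bound is 12.04% for 20/105 and 11.26% for 19/105, so the confidence-interval rule in SAP 3.10 agrees with the test. All of this concerns the investigator's ORR and does not involve BICR.

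**Inputs for the BICR comparison**

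- n = 105 investigator-evaluable patients (Protocol 10.1, SAP 2.2.2).
- R = BICR responders among those n, for illustration: 25 (23.8%, close to the 24% design rate) and 33 (31.4%, the investigator ORR that Protocol 10.5 reports for earlier patients who would have been eligible).
- k = patients among the n who are not measurable per BICR. Not in the documents; 0, 5 and 10 are assumed.
- c = BICR CRs among those k. Also assumed.

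**Formulas.** ORR on the common set = R/n. ORR on the BICR set, as planned = (R − c)/(n − k).

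**Results with c = 0**

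| R | common set, n = 105 | k = 5 | k = 10 |
|---|---|---|---|
| 25 | 25/105 = 23.8% (95% CI 16.0% to 33.1%) | 25/100 = 25.0% (+1.2 points) | 25/95 = 26.3% (+2.5 points) |
| 33 | 33/105 = 31.4% | 33/100 = 33.0% (+1.6 points) | 33/95 = 34.7% (+3.3 points) |

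With k = 0, and nobody entering the set, the two rates are identical.

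**Direction.** Dropping k patients raises the rate only if c/k is below R/n. At R = 25 the break-even is c = 5 × 25/105 = 1.2 for k = 5, and 10 × 25/105 = 2.4 for k = 10. So with k = 5, one CR gives 24/100 = 24.0%, still slightly up, and two give 23/100 = 23.0%, which is down. With k = 10, two CRs give 23/95 = 24.2% and three give 22/95 = 23.2%. Upward is the expected direction but it is not guaranteed.

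**Can planned outputs recover the common-set rate?** SAP 4.2.2 reports the size of each population. Suppose the sizes are 105 and 100, BICR shows 25/100, and patients only left. The common-set rate is then (25 + c)/105: 25/105 = 23.8% if c = 0, or 27/105 = 25.7% if c = 2. The counts alone do not settle it.

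**Patients entering the BICR set.** Someone measurable per BICR only would have to be treated without investigator-measurable disease, contrary to inclusion criterion 7, and Protocol 3.1.2 and 12.7 rule out waivers. Protocol 10.1 does leave room for about 110 − 105 = 5 treated but non-evaluable patients: "A total of approximately 110 patients will be enrolled to achieve 105 efficacy evaluable patients". Nothing suggests that central review would find them measurable. This is a remote case; reporting their number is enough.

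**The case against.** The strongest reply is that nothing here is an error. Each reader's responders are divided by that reader's evaluable patients, and SAP 3.12.3, 5.1.1.1 and 5.5 agree with one another. Protocol 10 describes one Efficacy Evaluable Population not split by reader, but Protocol 10.4 lets the SAP depart from it. Judging baseline measurability is also part of the central read, so some change of set comes with a change of reader. All of this stands, and it is why the planned analysis should remain.

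A second reply is that the information will exist anyway. SAP 5.6 plans listings of lesion assessments and derived best response, and SAP 4.2.2 gives the population counts. This helps only in part: the listings do not expressly name BICR reads, and no common-set summary is planned. The independent review charter was not available and may settle how patients without central target lesions are read, but the SAP fixes the denominator.

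A third reply is that a common-set rate is itself not neutral, because it retains patients whom BICR cannot call PR. That is correct. It is a reason to show both rates, and to tabulate separately the patients measurable by both readers.

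A reader might infer something stronger: that exclusions could carry the BICR result past 12%. Arithmetically, 19 responders have a lower bound of 11.3% on 105 and 12.1% on 98. The documents do not support treating that as a decision problem. SAP 3.10 applies the 12% rule to the primary endpoint, which is the investigator's ORR, and SAP 3.11.2 plans no formal testing of secondary endpoints.

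**Conclusion.** The point holds as an inexpensive improvement with a modest effect. BICR ORR is planned only on the BICR-measurable set, so the blinded check of the primary endpoint mixes a change of reader with a change of denominator, probably in the upward direction. On assumed losses of 5 or 10 of 105 with no BICR CR among them, the shift is 1.2 or 2.5 points from 23.8%, and 1.6 or 3.3 points from 31.4%. That is well inside the sampling uncertainty of a single ORR in a trial of this size.

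These sizes rest on counts that the documents do not give; the true shift may be zero, and it reverses if the patients who leave include enough BICR CRs. It should not be read as a flaw in the primary analysis, as evidence that the BICR set was chosen to flatter the result, or as grounds for dropping the reader-specific analysis.

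**What to change.** Keep the BICR analysis as planned and add to SAP 5.5:

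*BICR ORR will also be calculated on the investigator-defined Efficacy Evaluable population; patients not measurable per BICR count as non-responders unless BICR assigns a confirmed CR.*

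Add a cross-table of confirmed response, investigator by BICR, on that same population, with a separate row for patients not measurable per BICR. Agreement among patients measurable by both readers can then be read from the remaining rows. State the number of patients measurable per BICR only.

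**Cost.** One extra row and one table. The added BICR ORR will probably be slightly lower than the planned one: by 1.2 or 2.5 points at 25 responders, or 1.6 or 3.3 points at 33, under the assumptions above. The non-responder rule tilts it down, so both versions should appear side by side. If the review charter does not already require it, post-baseline scans of the few patients without BICR target lesions would need central reading. Protocol 7.13.1 already sends all scans to the central vendor, so no new imaging is needed.

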3.12.4. CA-125-Evaluable Population

The CA-125-Evaluable population is defined as all patients in the Safety population whose pretreatment sample is ≥ 2.0 times the upper limit of normal (ULN), within 2 weeks prior to first dose of MIRV, and who have at least 1 post-baseline CA-125 evaluation.

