- ^m If a patient discontinues before documentation of PD, a tumor assessment and CA-125 will be assessed at the EOT or 30-Day Follow-up visit, if not performed within the previous 6 weeks. Tumor assessments and CA-125 will continue to be performed every 12 (\pm 3) weeks until PD is documented per RECIST 1.1 or the patient starts new anticancer therapy. Patients who discontinue MIRV for reasons other than progressive disease (PD) will continue with tumor assessments until documentation of PD or the start of a new anticancer therapy, whichever comes first. Prior to Week 36 (from Cycle 1, Day 1), assessments should occur every 6 weeks (\pm 1 week) as allowed by local requirements but must occur at an interval of no more than 12 weeks. After Week 36, assessment will occur every 12 weeks (\pm 3 weeks) until documentation of PD, death, the start of new anticancer therapy, or patient's withdrawal of consent (whichever occurs first).

- ⁿ CA-125 will be measured at the time of every tumor assessment (± 4 days) (responses will be confirmed according to GCIG criteria [Appendix C](#)).
- ^o Only AEs/SAEs which are considered related to a study procedure (ie blood draw or fresh tumor biopsy) will be captured during the Pre-screening period, ie from the time of signing the Pre-screening consent (if one is utilized) until the signing of the main study informed consent, or until the patient is determined to be a screen failure.
- ^p Blood samples for PK analysis will be taken within 1 hour after MIRV infusion on Day 1 of Cycles 1 and 3, and on Day 8 (± 24 hours) of Cycles 1 and 3. Samples will also be collected prior to dosing on Day 1 of Cycles 2 and 4, and EOT and also at the 30-Day Follow-up, if feasible.
- ^q Immunogenicity will be assessed in PK samples collected prior to dosing (predose) on C1D1, C2D1, C4D1, at EOT, and 30-Day Follow-up.
- ^r Survival follow-up assessments will occur every 3 months (± 1 month) until death, the patient is lost to follow-up or withdrawal of consent for survival follow-up, or EOS (whichever comes first). These assessments may be conducted by telephone. Information on the start of new anticancer therapy (including start date, therapy type/name, and response on treatment) should be collected. Additional survival follow-up calls may occur periodically if needed for regulatory requests or at time of database lock for either primary or final analysis.

TABLE OF CONTENTS

SPONSOR SIGNATURE PAGE	2
SPONSOR CONTACT LIST	3

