5.6.3. Withdrawal of Consent

The patient or legally authorized representative acting on behalf of the patient is free to withdraw consent to study treatment and/or participation in the study at any time irrespective of the reason. The Investigator must make every effort (eg, telephone, email, letter) to determine the primary

reason for this decision and record this information. Study treatment must be discontinued, and no further assessments conducted. Further attempts to contact the patient are not allowed unless safety findings require communication or follow-up. If the patient or legally authorized representative withdraws consent for disclosure of future information, the Sponsor may retain and continue to use any data collected before withdrawal of consent. All biological samples that have been already collected will be retained and analyzed at a later date. The patient or legally authorized representative may request destruction of any samples, and the Investigator must document this in the site study records. The SAP will specify how early withdrawals from treatment will be accounted for in the analyses of efficacy endpoints. Patients who have withdrawn from the study cannot be re-treated in the study and their inclusion and patient number must not be reused.

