This CA-125 response definition has been produced to evaluate relapse therapy. If assessing therapy that includes two treatment modalities for relapse (eg, surgery and chemotherapy), any CA-125 response results from both treatments. CA-125 cannot distinguish between the effects of each treatment. To calculate response rates in protocols, an ITT analysis should be used that includes all patients with an initial CA-125 level of at least twice the ULN as eligible and evaluable. In addition to calculating response rates in protocols, it is advisable to record those patients who have both a CA-125 response and whose CA-125 level falls to within the normal range.

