2.1.3.2. Key Secondary Endpoint

• Duration of response (DOR), defined as the time from initial Investigator-assessed response (CR or PR) until PD as assessed by the Investigator.

2.1.3.2.1. Additional Secondary Endpoints:

- Treatment-emergent adverse events (TEAEs) and laboratory test results, physical examination, or vital signs.
- CA-125 response determined using the GCIG criteria defined in Protocol IMGN853-0417, Appendix C. CA-125 response per GCIG criteria will be determined programmatically.
- Progression-free survival (PFS): defined as the time from first dose of MIRV until Investigator-assessed radiological PD or death, whichever occurs first.
- Overall survival (OS), defined as the time from first dose of MIRV until the date of death. Patients alive at the time of analysis will be censored at the last date known to be alive.
- ORR, DOR, and PFS by blinded independent central review (BICR) will be summarized as sensitivity analysis.

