5.1.4. GCIG CA-125 Response

A GCIG CA-125 response is defined as $a \ge 50\%$ reduction in CA-125 levels from baseline. The response must be confirmed and maintained for at least 28 days. The CA-125 response will be conducted using the CA-125-Evaluable population. The date of response corresponds to the date when the CA-125 level is first reduced by 50%. The summary table for CA-125 will include the number (percentage) of patients in the CA-125-Evaluable population, and that number will then be used as the denominator for CA-125 response rate.

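### The CA-125 response rate drops patients with no post-baseline CA-125 from its denominator, unlike Appendix C and the SAP's own ORR rule, so it can be raised but never lowered

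*SAP*

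**What the plan says.** SAP 3.12.4 defines the CA-125-Evaluable population by three conditions on the Safety population: a pretreatment value of at least 2 x ULN, taken within 2 weeks before first dose, "and who have at least 1 post-baseline CA-125 evaluation". SAP 5.1.4 reports the size of that population and says "that number will then be used as the denominator for CA-125 response rate". The same section requires a fall of at least 50% from baseline and adds: "The response must be confirmed and maintained for at least 28 days".

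SAP 2.1.3.2.1 lists the endpoint as "CA-125 response determined using the GCIG criteria defined in Protocol IMGN853-0417, Appendix C". On how to compute a rate, Appendix C of the protocol says "an ITT analysis should be used that includes all patients with an initial CA-125 level of at least twice the ULN". It sets no post-baseline condition. Its other grounds for calling a patient not evaluable are mouse antibodies and recent interference with the peritoneum or pleura.

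For the primary endpoint, SAP 5.1.1.1 states: "Patients without at least 1 post-baseline RECIST assessment will be treated as non-responders". Those patients stay in the ORR denominator.

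**The concern.** The SAP gives the word evaluable a narrower meaning than the source it cites, and does not say why. It also treats the same kind of missing information in three ways:

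- A patient with no post-baseline scan is an ORR non-responder.
- A patient with a single post-baseline CA-125 cannot satisfy the 28-day confirmation, yet stays in the CA-125 denominator as a non-responder.
- A patient with no post-baseline CA-125 is removed from the CA-125 denominator.

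The removed patients are unlikely to be a random sample. CA-125 is drawn with the tumor assessments (Protocol 7.13.2), so the first scheduled on-treatment value comes at about Week 6. Early deaths, early consent withdrawals and missed samples are the likeliest ways to have none. At stake is a descriptive rate from a single-arm trial. It would be reported as following the GCIG criteria while standing on a denominator that those criteria do not describe.

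**Working it through.** **Is the post-baseline clause the only difference in the denominator?** The baseline threshold and the 2-week window in SAP 3.12.4 match Appendix C. Under Protocol 5.2.1 a patient counts as enrolled only after at least one dose, so the Safety population with a qualifying baseline is in effect the intention-to-treat set that Appendix C describes. SAP 3.12.4 does not apply Appendix C's mouse-antibody and peritoneal or pleural exclusions. That is a separate matter. The post-baseline clause is what the SAP adds.

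**Direction.** Let N be the patients with a qualifying baseline, m those of them with no post-baseline CA-125, and x the confirmed responders. A confirmed fall of at least 50% needs post-baseline samples, so none of the m patients can be among the x.

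- Appendix C rate = x / N
- SAP rate = x / (N - m)
- Ratio = N / (N - m) = 1 / (1 - f), with f = m / N

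The ratio is 1 if m = 0 and above 1 otherwise. It is never below 1.

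**Size.** The documents give no planned rate, N or m for this endpoint, so there is no figure of the plan's own to reproduce and the values of f are assumptions. Protocol 1.6.2 reports a 53% CA-125 response in response-evaluable MIRV patients in the earlier Phase 3 trial, without defining that term. Both readings are therefore shown.

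| f = m/N | Factor 1/(1-f) | If 53% is a SAP-type rate: Appendix C rate = 53(1-f) | Difference (points) | If 53% is an Appendix C rate: SAP rate = 53/(1-f) | Difference (points) |
|---|---|---|---|---|---|
| 0 | 1.000 | 53.00% | 0 | 53.00% | 0 |
| 2% | 1.020 | 51.94% | 1.06 | 54.08% | 1.08 |
| 5% | 1.053 | 50.35% | 2.65 | 55.79% | 2.79 |
| 10% | 1.111 | 47.70% | 5.30 | 58.89% | 5.89 |

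**In whole patients**, assuming N = 90, m = 5 and x = 45, with Clopper-Pearson intervals as SAP 5.3.2 specifies:

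- SAP rate: 45/85 = 52.9% (95% CI 41.8 to 63.9)
- Appendix C rate: 45/90 = 50.0% (95% CI 39.3 to 60.7)
- Difference: 2.9 points, against a half-width of (63.9 - 41.8)/2, or about 11 points

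With m = 1 or 2 the SAP rate would be 45/89 = 50.6% or 45/88 = 51.1%.

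**Wider range.** With assumed N from 70 to 105, Appendix C rates of about 40% to 53%, and about 2% to 15% of patients without a post-baseline value (rounded to whole patients), the increase runs from 0.6 to 9.6 points. At about 5% missing it is 2.0 to 3.2 points.

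**Who is affected.** Protocol 5.6.3 says of a patient who withdraws consent: "Study treatment must be discontinued, and no further assessments conducted". Such a patient, if early enough, has no post-baseline value, and the same is true of an early death. For patients who discontinue before documented progression, footnote m to Protocol Table 2 says "a tumor assessment and CA-125 will be assessed at the EOT or 30-Day Follow-up visit, if not performed within the previous 6 weeks". That recovers some of them. Read literally, though, a screening sample taken up to 14 days before first dose could itself fall within the previous 6 weeks for a patient who stops in the first few weeks.

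**The case against.** Protocol 10.4 lets the SAP name a population other than the Efficacy Evaluable one, and the SAP does so in advance. Appendix C is advisory on this point, and the trial does not adopt all of it: the appendix allows progression by CA-125, whereas the SAP's PFS uses radiological progression only. The ORR rule belongs to the primary, tested endpoint and is nowhere extended to CA-125. CA-125 response has no formal test (SAP 3.11.2). The affected group is narrow, its size is hypothetical, and the illustrated shift lies well inside the confidence interval. Population counts (SAP 4.2.2 and 5.1.4) and the CA-125 listings (SAP 5.6) would let a reader rebuild the other rate.

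Most of this stands, and it limits the point. This is an unexplained departure from a recommendation, not a breach, and it changes nothing if every qualifying patient has a post-baseline value. Three parts do not answer it:

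- A confidence interval describes sampling error. It does not excuse a shift that can go only one way.
- The planned count mixes patients excluded for a low baseline with patients lacking follow-up. The listings allow reconstruction, but the headline rate stays on the selected denominator.
- The only planned sensitivity analyses are ORR, DOR and PFS by BICR (SAP 5.5), so the all-qualifying-baseline rate is not planned anywhere.

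**Conclusion.** The concern holds. The SAP's CA-125 denominator departs without explanation from the Appendix C recommendation and from the way the SAP handles unassessed patients for ORR. The direction is certain: the rate is raised or left unchanged. The size is not known from the documents. It depends wholly on m/N and would be a few points if about 5% of qualifying patients lack a post-baseline value. A few exclusions would weigh more in the subgroup analyses of SAP 5.4. The consequence is confined to an untested additional secondary endpoint, and the primary ORR test is untouched. The change is worth making because it is cheap and removes a one-sided selection from a rate that has no control arm beside it.

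**What to change.** In SAP 3.12.4, delete the clause "and who have at least 1 post-baseline CA-125 evaluation" and state that patients with a qualifying baseline CA-125 and no post-baseline value count as non-responders, parallel to the ORR rule. The present set may be kept as a labelled sensitivity analysis. In either case, report the number of qualifying patients with no post-baseline CA-125 separately from those excluded for a baseline below 2 x ULN. SAP 5.3.2 calls the population by a slightly different name (CA-125 Response-Evaluable), which can be aligned in the same edit.

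The cost is one SAP clause and no new data. SAP 1.1 allows changes before final database lock. The reported rate may be slightly lower, and is unchanged if nobody lacks a post-baseline value.
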